8.3 RECORDS

CRFs for individual patients will be provided by the sponsor. See section [4.1.5.2](#) for rules about emergency code breaks. For drug accountability, refer to section [4.1.8](#).

8.3.1 Source documents

In accordance with regulatory requirements, the investigator should prepare and maintain adequate and accurate source documents and trial records that include all observations and other data pertinent to the investigation on each trial patient. Source data as well as reported data should follow the "ALCOA principles" and be **attributable, legible, contemporaneous, original and accurate**. Changes to the data should be traceable (audit trail).

Data reported on the CRF must be consistent with the source data or the discrepancies must be explained.

The current medical history of the patient may not be sufficient to confirm eligibility for the trial and the investigator may need to request previous medical histories and evidence of any diagnostic tests. In this case, the investigator must make at least one documented attempt to retrieve previous medical records. If this fails, a verbal history from the patient, documented in their medical records, would be acceptable.

If the patient is not compliant with the protocol, any corrective action e.g. re-training must be documented in the patient file.

For the CRF, data must be derived from source documents, for example:

- Patient identification: gender, year of birth (in accordance with local laws and regulations)

- Patient participation in the trial (substance, trial number, patient number, date patient was informed)
- Dates of patient's visits, including dispensing of trial medication
- Medical history (including trial indication and concomitant diseases, if applicable)
- Medication history
- Adverse events and outcome events (onset date (mandatory), and end date (if available))
- Serious adverse events (onset date (mandatory), and end date (if available))
- Concomitant therapy (start date, changes)
- Originals or copies of laboratory results and other imaging or testing results, with proper documented medical evaluation
- Completion of patient's participation in the trial" (end date; in case of premature discontinuation document the reason for it).
- Prior to allocation of a patient to a treatment into a clinical trial, there must be documented evidence in the source data (e.g. medical records) that the trial participant meets all inclusion criteria and does not meet any exclusion criteria. The absence of records (either medical records, verbal documented feedback of the patient or testing conducted specific for a protocol) to support inclusion / exclusion criteria does not make the patient eligible for the clinical trial.

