4.3.1.2 Safety Variables

Missing safety data will generally not be imputed.

However, safety assessment values of the form of “<x” (i.e. below the lower limit of quantification) or “>x” (i.e. above the upper limit of quantification) will be imputed as “x” in the calculation of summary statistics but displayed as “<x” or “>x” in the listings.

Additionally, AE that have missing causality will be assumed to be related to study drug.

Missing severity of an AE will be assumed to be severe. Occurrence of this is unlikely, as severity and causality are mandatory fields in the eCRF.

CONFIDENTIAL

Project Document Version No. 2.0

Effective Date: 30 Jan 19

Project Document Effective Date: Date of last signature

Related to: [REDACTED]

Page 15 of 41

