4.10.1.6 Vomiting and Nausea

Cases of vomiting and nausea can occur following intake of atomoxetine. Vomiting and nausea events will be captured as AEs and the sites / patients will be encouraged to report start and end times of these events to identify impact on study drug as well as impulsivity testing. Such AEs will be summarized separately (please refer to Section 4.11.1).

If the start time of the AE of vomiting or nausea is missing, it will be assumed not to have affected treatment or impulsivity assessment.

On Day 1 and Day 14, occurrence of vomiting post-dose, but before PK sampling will lead to exclusion of any following PK sample from summary statistics (see Section 4.10.5) for the PK concentrations of that day. E.g., if vomiting occurs on Day 14 post-dose, but before the first sampling time on Day 14, both Day 14 samples (pre- and post-impulsivity testing) will be excluded from PK summaries. Such events will be reviewed during AE review and the preliminary and/or interim analysis or at the Data Review Meeting prior to database lock.

 CONFIDENTIAL

Project Document Version No. 2.0

Effective Date: 30 Jan 19

Project Document Effective Date: Date of last signature

Related to: 

Page 22 of 41

It is expected that vomiting and nausea can have influence on the conduct of impulsivity assessments. For the primary analysis, occurrence of these events will not lead to exclusion from the analysis and this event is handled by the treatment policy strategy.

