4.10.5 Pharmacokinetics

4.10.5.1 Pharmacokinetic Concentrations

All collected pharmacokinetic concentrations of atomoxetine will be listed for each participant and by treatment (at least the Placebo samples for the timepoints Visit 3, Planned Time 2:00 hours and Visit 4, 314:00 hours will be measured) in the TS. Listings will include actual sampling times relative to dose administration, the subject's inclusion in the PK-PPS and concentrations' inclusion/exclusion from the analysis with the reason for exclusion. Plasma concentrations below the LLOQ will be presented as BLQ in the listings.

Plasma concentration data of a patient will be included in the PK analyses (i.e. descriptive summaries), if they are not flagged for exclusion due to a protocol deviation relevant to the evaluation of PK (in a Data Review Meeting prior to database lock) or due to PK non-evaluability (as revealed during data analysis, based on the criteria specified below). Only concentrations within the validated concentration range will be used. Handling of pharmacokinetic concentrations will be done according to BI standards. Exclusion of a patient's data will be documented in the Clinical Trial Report and excluded data listed together with the reason for exclusion.

Reasons for data exclusions considered include, but are not limited to:

- Vomiting occurs on Day 1 or 14 post-dose, but prior to or during a PK sampling and will be finally confirmed during AE review (see Section 4.10.1.6)
- PK samples are collected more than 30 minutes before the nominal time of 2:00 hours after study drug administration (start time of impulsivity testing), and / or more than 30 minutes after the nominal time of 3:00 hours after study drug administration (end of impulsivity testing) after study drug administration on Day 1 and 14 and will be confirmed during PK data review
- No study drug intake on Day 1 or 14

CONFIDENTIAL

Project Document Version No. 2.0

Effective Date: 30 Jan 19

Project Document Effective Date: Date of last signature

Related to: [REDACTED]

[figure not shown]
Page 34 of 41

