4.11.1 Adverse Events

- An AE is defined as any untoward medical occurrence in a patient or clinical investigation subject administered a medicinal product and which does not necessarily have to have a causal relationship with this treatment.

An AE can therefore be any unfavourable and unintended sign (including an abnormal laboratory finding), symptom, or disease temporally associated with the use of a medicinal product, whether considered related or not.

The following should also be recorded as an AE in the CRF and Boehringer Ingelheim SAE form (if applicable):

- Worsening of the underlying disease or of other pre-existing conditions.
- Changes in vital signs (body temperature, systolic and diastolic blood pressure, and pulse rate), ECG, physical examination (QTc interval and interpretation, clinically relevant abnormal findings), assessment of suicidality via C-SSRS and laboratory test results (hematology, chemistry, enzymes, electrolytes, substrates, pregnancy test, urinalysis [at screening]), if they are judged clinically relevant by the investigator.
- If such abnormalities already exist prior to trial inclusion, they will be considered as baseline conditions and should be collected in the eCRF only.
- A TEAE is defined as an AE that begins or that worsens in severity after at least one dose of the study drug has been administered. Only AEs with start date until 4 days after the last dose of study drug are considered as TEAEs.
- An SAE is defined as any AE, which fulfils at least one of the following criteria:
 - results in death,
 - is life-threatening, which refers to an event in which the patient was at risk of death at the time of the event; it does not refer to an event that hypothetically might have caused death if more severe,
 - requires inpatient hospitalisation or prolongation of existing hospitalisation

CONFIDENTIAL

Project Document Version No. 2.0

Effective Date: 30 Jan 19

Project Document Effective Date: Date of last signature

Related to: [REDACTED]

Page 36 of 41

- results in persistent or significant disability or incapacity,
- is a congenital anomaly / birth defect,

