- is deemed serious for any other reason if it is an important medical event when based on appropriate medical judgement which may jeopardise the patient and may require medical or surgical intervention to prevent one of the other outcomes listed in the above definitions. Examples of such events are intensive treatment in an emergency room or at home for allergic bronchospasm, blood dyscrasias or convulsions that do not result in hospitalisation or development of dependency or abuse.
- Adverse events will be coded using the MedDRA Version 24.1 or higher.
- Listings and tables showing AEs will be based on the TS.
- Where dates are missing or partially missing, AEs will be assumed to be treatment-emergent, unless there is clear evidence (through comparison of partial dates) to suggest that the AE started prior to the first dose of study drug.
- Adverse event summaries will be ordered in terms of decreasing frequency for SOC, and PT within SOC, in the study drug treatment group, and then alphabetically for SOC, and PT within SOC.
- For each subject and each AE, the worst severity recorded will be attributed and used in the by-severity summaries. Similarly, the worst causality (most related to treatment) will be attributed and used in the by-causality summaries. If severity or causality is missing, the worst case will be assumed.

AE information will be listed per subject including the MedDRA SOC, PT and reported term. The listing will include at least age, sex, race of the patient and start/end date/time, relationship to study drug per the investigator's opinion, severity, seriousness, outcome, duration, leading to dropout, action taken of the event.

The following descriptive summaries will be produced for TEAEs with percentages based on the number of subjects in the TS:

- A summary of the number and percentage of subjects reporting a TEAE by seriousness, relationship to study drug, maximum severity, death and leading to discontinuation for each treatment group
- A summary of the number and percentage of subjects reporting a TEAE by treatment group, SOC and PT including the number of events.
- A summary of the number and percentage of subjects reporting an SAE by treatment group, SOC and PT including the number of events.

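### Vomiting with no recorded start time is assumed to be harmless, so PK samples taken after a possibly lost dose stay by default in the atomoxetine concentration summary (minor)

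*Protocol*

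**What the plan says.** **Recording of onset.** Protocol 8.3.1 gives a list that opens with "For the CRF, data must be derived from source documents, for example" and contains the item "Adverse events and outcome events (onset date (mandatory), and end date (if available". Only the date is marked as mandatory. For vomiting and nausea, SAP 4.10.1.6 says that "the sites / patients will be encouraged to report start and end times of these events". SAP 4.3.1.2 states that "severity and causality are mandatory fields in the eCRF" and does not name onset time. The AE listing in SAP 4.11.1 nevertheless includes "start/end date/time, relationship to study drug", so times are at least foreseen.

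**PK exclusion.** SAP 4.10.1.6 drops from that day's summary statistics any PK sample that follows post-dose vomiting on Day 1 or Day 14. SAP 4.10.5.1 repeats this as an exclusion reason: "Vomiting occurs on Day 1 or 14 post-dose, but prior to or during a PK sampling". Where the start time of such an event "is missing, it will be assumed not to have affected treatment or impulsivity assessment".

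**Treatment-emergence.** SAP 4.11.1 defines a TEAE as an AE that "begins or that worsens in severity after at least one dose of the study drug" has been given. AEs with missing or partial dates default to treatment-emergent unless there is clear evidence to the contrary.

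**The concern.** The exclusion rule works only if the clock time of the vomiting is known, and the plan does not clearly require it. When the time is absent, the SAP assumes the answer that keeps the sample. The same SAP section opens by saying that these events can follow atomoxetine intake, so a same-day untimed event could well be post-dose.

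This default also differs from how the SAP treats other gaps in AE data. Missing causality is taken as related, missing severity as severe, and incomplete dates as treatment-emergent. Untimed vomiting gets the benign assumption.

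What is at stake is the descriptive summary of plasma concentrations. Protocol 5.3.1 says the samples may be used to confirm adequate exposure. SAP 4.10.1.4 allows a preliminary PK analysis to confirm compliance and the suitability of the measurements for the primary analysis. Both are optional uses. A retained low value after a lost dose makes exposure under a dose that was kept down look lower than it was.

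A related gap in wording concerns AEs dated Day 1 with no time. The TEAE definition needs to know whether onset came after the first dose. The default in SAP 4.11.1 speaks of dates, and the table in SAP 4.3.1.3 is introduced as covering date/time but has scenarios only for missing or partial dates. A complete Day 1 date without a time is not named in either. SAP 4.2.1 does settle the equivalent question for untimed baseline assessments on the day of first intake.

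**Working it through.** The plan states no figure on this point, so there is nothing to reproduce. The check is a reading of the rules, followed by an illustration of size.

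**Step 1: apply the rules to one case.** A patient has vomiting dated Day 14 with no start time, and samples at about 2 h and 3 h post-dose.
- The exclusion rule needs vomiting after the dose and before or during sampling. With no time, this cannot be shown.
- The missing-time rule then assumes no effect on treatment.
- Default result: both post-dose samples stay in the summary.
- For the primary endpoints, SAP 4.10.1.6 and 4.10.2 handle vomiting by treatment policy. The score is used either way.
- For the pill and compliance summary (SAP 4.9.1, 4.9.2), intake is counted by pills and days with no vomiting rule. A vomited dose counts as taken whether or not its time is known.

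**Step 2: effect on the PK summary.** Inputs: n = 40 atomoxetine patients (Protocol synopsis, 40 per arm). The number of affected patients k and the fraction f of the usual concentration are assumptions, because the documents give neither.

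The geometric mean is the exponential of the mean log concentration (SAP 4.10.5.1). Multiplying k of n values by f multiplies it by f^(k/n). If the affected patients would otherwise sit at the mean, the arithmetic mean changes by −(1 − f)·k/n.

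| k | f | Geometric mean | Arithmetic mean |
|---|---|---|---|
| 1 | 0.5 | −1.7% | −1.25% |
| 1 | 0.1 | −5.6% | −2.25% |
| 1 | 0.01 | −10.9% | −2.48% |
| 2 | 0.5 | −3.4% | −2.5% |
| 2 | 0.1 | −10.9% | −4.5% |
| 2 | 0.01 | −20.6% | −4.95% |
| 4 | 0.5 | −6.7% | −5.0% |
| 4 | 0.1 | −20.6% | −9.0% |
| 4 | 0.01 | −36.9% | −9.9% |

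For example, with k = 1 and f = 0.1: 0.1^(1/40) = 0.944, a fall of 5.6%.

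**Step 3: limit on the Day 14 fall.** Protocol 1.2 gives half-lives of 4.5 to 19 h. If the Day 14 dose is lost entirely but earlier doses were taken, simple first-order decay over the 24 h since the same clock time on Day 13 gives a fold reduction of 2^(24/t½):
- t½ = 4.5 h: 2^(24/4.5) ≈ 40-fold, so one patient in 40 lowers the geometric mean by 1 − 40^(−1/40) ≈ 8.8%.
- t½ = 19 h: 2^(24/19) ≈ 2.4-fold, a lowering of about 2.2%.

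The f = 0.01 rows therefore do not fit Day 14. On Day 1 there is no earlier trial dose. There the lower bound is the LLOQ/2 substitution of SAP 4.10.5.2, and the documents reviewed do not state the LLOQ.

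**Step 4: untimed Day 1 AEs.** A patient whose only AE is an untimed Day 1 event moves the arm's TEAE percentage by 1/40 = 2.5 points, depending on how it is classified.

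**The case against.** The strongest reply is that the default may often be right. Patients are on site through the 2 h and 3 h samples, and until about 4 h after dosing. Vomiting that could spoil a sample would therefore usually happen in front of staff, who can note the time. An untimed event may more often have occurred at home, before the visit or after discharge, where it could not have affected that day's samples. This stands as an argument against simply reversing the default, since a reversal could discard valid data. It also shows that the time is easy to obtain for the events that matter.

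Second, SAP 4.10.1.6 and 4.10.5.1 send vomiting events to AE review and the Data Review Meeting, and the listed exclusion reasons are not exhaustive. This is a partial safeguard. The written default still tells reviewers to assume no effect, and Protocol 4.1.5.1 leaves sponsor statisticians and pharmacokineticists unblinded, so a fixed rule is preferable to discretion.

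Third, the consequences are small. No PK parameters are calculated (SAP 4.10.5.3) and no PK/PD evaluation is planned (Protocol 5.3.4). Low values in patients who vomited also reflect the real exposure of patients kept in the primary analysis. This stands, and it is the reason for the minor rating and for showing both summaries.

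A reader might also infer three stronger points that the documents do not support:
- **That the eCRF leaves onset time optional for all AEs.** The list in Protocol 8.3.1 gives examples and is not the eCRF specification, which is not among the documents. The firm basis is the encouragement in SAP 4.10.1.6, which covers vomiting and nausea only.
- **That missing times keep lost doses in the treatment exposure summary.** That summary counts pills and keeps vomited doses even when they are timed.
- **That Day 1 AEs cannot be placed before or after first dose.** Only untimed ones are in question, and the SAP already leans towards treatment-emergent.

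**Conclusion.** The point holds and is minor. SAP 4.10.1.6 does not require the start time on which its own PK exclusion depends, and it fills the gap with an assumption that keeps the sample. The descriptive atomoxetine concentration summary on Day 1 or Day 14 can therefore be biased downward.

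For one affected patient in 40, the geometric mean falls by 5.6% if the value is 10-fold too low. On Day 14 the fall is about 2.2% to 8.8% across the protocol's half-life range if the whole dose is lost. These sizes rest on assumed fold reductions, or on first-order decay with all earlier doses taken. How often the case would arise cannot be judged, because neither a vomiting rate nor a missing-time rate is given.

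The primary ANCOVAs are not touched. For untimed Day 1 AEs, the secondary endpoint needs a clarifying sentence; it is not left without direction.

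**What to change.** 1. **Data collection.** For AEs starting on the on-site dosing days 1 and 14, require an onset time in the eCRF, or an indicator of before/after dose and before/after each PK sample. An indicator is enough for both rules and does not force staff to invent a clock time.
2. **SAP 4.10.1.6 and 4.10.5.1.** For vomiting on those days whose timing is still unknown, replace the no-effect assumption for PK. Flag that day's post-dose samples, present the concentration summary with and without them, and keep every value in the listing. The treatment-policy handling in the primary analysis stays as it is.
3. **SAP 4.11.1 (clarification).** Extend the treatment-emergent default to AEs dated Day 1 with no time, unless there is clear evidence of onset before the first dose.

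The cost is one eCRF edit check, a few SAP sentences and one extra PK summary. Because both versions of the summary are shown, no valid concentration is lost if an untimed event turns out to have been irrelevant.

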8.3.2 Direct access to source data and documents

The investigator / institution will allow site trial-related monitoring, audits, IRB / IEC review and regulatory inspections. Direct access must be provided to the CRF and all source documents / data, including progress notes, copies of laboratory and medical test results, which must always be available for review by the CRA, auditor and regulatory inspector (e.g. FDA). They may review all CRFs and informed consents. The accuracy of the data will be verified by direct comparison with the source documents described in section [8.3.1](#). The sponsor or delegate will also monitor compliance with the protocol and GCP.

8.3.3 Storage period of records

Trial site(s):

The trial site(s) must retain the source and essential documents (including ISF) according to contract or the local requirements valid at the time of the end of the trial (whatever is longer). Sponsor:

The sponsor must retain the essential documents according to the sponsor's SOPs.

8.4 EXPEDITED REPORTING OF ADVERSE EVENTS

BI is responsible to fulfil their legal and regulatory reporting obligation in accordance with regulatory requirements.

8.5 STATEMENT OF CONFIDENTIALITY AND PATIENT PRIVACY

Data protection and data security measures are implemented for the collection, storage and processing of patient data in accordance with the principles 7 and 12 of the WHO GCP handbook.

To ensure confidentiality of records and personal data, only pseudonymised data will be transferred to the sponsor by using a patient identification number instead of the patient's name. The code is only available at the site and must not be forwarded to the sponsor. In case patient's records will be forwarded e.g. for SAE processing or adjudication committees, personal data that can identify the patient will be redacted by the site prior to forwarding. Access to the patient files and clinical data is strictly limited: personalised treatment data may be given to the patient's personal physician or to other appropriate medical personnel responsible for the patient's welfare. Data generated at the site as a result of the trial need to be available for inspection on request by the participating physicians, the sponsor's representatives, by the IRB / IEC and the regulatory authorities.

A potential data security breach will be assessed regarding the implications for rights and privacy of the affected person(s). Immediate actions as well as corrective and preventive actions will be implemented. Respective regulatory authorities, IRBs / IECs and patients will be informed as appropriate.

8.5.1 Collection, storage and future use of biological samples and corresponding data

Measures are in place to comply with the applicable rules for the collection, biobanking and future use of biological samples and clinical data, in particular

- Sample and data usage have to be in accordance with the separate biobanking informed consent
- The BI-internal facilities storing biological samples from clinical trial participants as well as the external banking facility are qualified for the storage of biological samples collected in clinical trials
- An appropriate sample and data management system, incl. audit trail for clinical data and samples to identify and destroy such samples according to ICF is in place
- A fit for the purpose documentation (biomarker proposal, analysis plan and report) ensures compliant usage
- A fit for purpose approach will be used for assay / equipment validation depending on the intended use of the biomarker data
- Samples and / or data may be transferred to third parties and other countries as specified in the biobanking ICF

